3.1 General Study Design

This is a Phase 3, multicenter, randomized, prospective, double-masked, placebo-controlled, parallel-arm design. Subjects will be randomized to one of the following treatment arms at Visit 2 (Day 1) and will be instructed to follow a twice daily (BID) dosing regimen:

- Tanfanercept Ophthalmic Solution 0.25% (N~150)
- Placebo Ophthalmic Solution (N~150)

Approximately 300 subjects will be randomly assigned to one of two treatment groups (1:1) to receive either Tanfanercept Ophthalmic Solution 0.25% or Placebo Ophthalmic Solution as topical ophthalmic drops administered bilaterally twice daily (BID). The total number of expected participants, including screen failures, is approximately 857 subjects.

Information regarding subjects, Sponsor, Clinical Research Organizations, and site personnel will be masked and treatment group assignment will be unknown to subjects.

During the 14-day screening period, endpoint measurements will be taken to ascertain eligibility to enter the study. Those who qualify will be randomized to receive study drug in a double-masked fashion for 56 days. Subjects will self-administer drops BID.

Table 1 shows the scheduled study visits, planned study day (note that there is no Day 0 and that Day 1 corresponds to the day of randomization), the acceptable visit window for each study visit, and the analysis visit window.

Table 1. Scheduled Study Visits, Planned Study Days, and Visit Windows

Scheduled Visit	Planned Study Day	Visit Window	Analysis Visit Window
Visit 1	Day -14	± 2 days	Day -16 to Day -1
Visit 2	Day 1	N/A	N/A
Visit 3	Day 8	± 1 day	Day 2 to Day 11
Visit 4	Day 15	± 2 days	Day 12 to Day 21
Visit 5	Day 29	± 2 days	Day 22 to Day 43
Visit 6	Day 57	± 3 days	Day 44 to Day 60

Analysis visit windows will be implemented for efficacy analyses only. If a subject has multiple assessments/results reported within an analysis visit window, the following selection hierarchy will be implemented.

1. If results are reported at the planned study day and at an unscheduled visit, then the results reported on the planned study day will be selected.
2. If no results are reported on the planned study day, then the results/observation reported at the study day closest to the planned study day will be selected.

If there is a tie on the number of days prior to planned study day and post planned study day, then the results/observation reported prior to planned study day will be selected.

[figure not shown]

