2.6 Estimands

The primary analysis of the primary endpoints will use the Intent-to-Treat (ITT) population for the primary endpoints of Change from Baseline (CFB) of CCSS at Day 57 ± 3 and CFB of EDS-VAS at Day 57 ± 3 , and the primary analysis will be executed using mixed model repeated measures (MMRM) with multiple imputation methodology using the following estimand:

Estimand 1:

- Population:
 - ITT population
- Endpoints:
 - CFB in CCSS in the study eye at Day 57 ± 3 in the ITT population
 - CFB in EDS from VAS at Day 57 ± 3 in the ITT population
- Intercurrent events:
 - Discontinuation of study medications is ignored. Measures obtained after discontinuation of study medication will be analyzed. [treatment policy strategy]
 - Non-optimal compliance is ignored. Measures will be analyzed regardless of treatment compliance. [treatment policy strategy]
 - Use of prohibited concomitant medications is ignored. Measures obtained after use of prohibited concomitant medications will be analyzed. [treatment policy strategy]
 - Withdrawal due to lack of efficacy or adverse events: Missing values assumed to be missing not at random will be multiply imputed using placebo group-based PMM imputation. [hypothetical strategy]
 - Missing data with withdrawal or withdrawal due to reasons other than lack of efficacy or adverse events: Missing values assumed to be missing at random will be multiply imputed using randomized treatment group-based MCMC imputation. [hypothetical strategy]
- Population-level summary:
 - Difference in the mean CFB in CCSS in the study eye at Day 57 ± 3 between Tanfanercept and placebo in the ITT population.
 - Difference in the mean CFB in EDS (VAS) at Day 57 ± 3 between Tanfanercept and placebo in the ITT population.

If the rate of missing data for EDS-VAS is imbalanced between treatment groups (demonstrated by Fisher's exact test with a p-value of <0.05) and the rate of missing data for EDS-VAS is $\geq 10\%$ in all subjects, then the primary analyses will utilize the ITT population using the permutation test with trimmed means methodology, as detailed in Estimand 2.

Estimand 2:

- Population:
 - ITT population
- Endpoint:
 - CFB in CCSS in the study eye at Day 57 ± 3 in the ITT population
 - CFB in EDS from VAS at Day 57 ± 3 in the ITT population
- Intercurrent event:
 - Discontinuation of study medications is ignored. Measures obtained after discontinuation of study medication will be analyzed. [treatment policy strategy]

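### The Visit 6 analysis window reaches 13 days early but stops 3 days late, so an only Week 8 result after Day 60 has no analysis visit and, read naturally, is treated as missing

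*SAP*

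**What the plan says.** SAP section 3.1, Table 1, gives each visit a visit window and a separate analysis window. Visit 6 is planned for Day 57 with a visit window of ± 3 days and an analysis window of "Day 44 to Day 60". The Visit 5 analysis window is "Day 22 to Day 43". On scope, the SAP says: "Analysis visit windows will be implemented for efficacy analyses only". SAP section 13.1 computes the primary change from baseline by reference to section 3.1.

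The only handling rule that follows covers several results inside one window: "If a subject has multiple assessments/results reported within an analysis visit window, the following selection hierarchy will be implemented". Nothing is said about a result that falls inside no window.

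SAP section 2.6 defines the Estimand 1 endpoint as "CFB in CCSS in the study eye at Day 57 ± 3 in the ITT population", with the same timing for EDS. Under the treatment-policy strategy for three named events it says, for stopping study drug, "Measures obtained after discontinuation of study medication will be analyzed" and, for dosing compliance, "Measures will be analyzed regardless of treatment compliance"; prohibited medication is treated in the same way. For missing values not linked to lack of efficacy or adverse events: "Missing values assumed to be missing at random will be multiply imputed using randomized treatment group-based MCMC imputation".

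The protocol has no analysis windows.

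**The concern.** Visits 3 to 5 have adjoining windows that run past their visit-window limits, so a late visit there still finds a place. Visit 6, the only primary timepoint, does not have this. A value 13 days early counts as Week 8, and a value 4 days late has no analysis visit. If the table is programmed as written, an observed primary outcome in an ITT subject is replaced by imputation because of a scheduling deviation. That gives up information, adds to a missing-data rate that helps choose between two primary methods, and could bias the contrast if lateness is related to treatment or outcome.

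**Working it through.** **1. Windows in Table 1 (day arithmetic).**

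| Visit | Planned day | Visit window | Analysis window | Days early | Days late |
|---|---|---|---|---|---|
| 3 | 8 | ± 1 | 2–11 | 6 | 3 |
| 4 | 15 | ± 2 | 12–21 | 3 | 6 |
| 5 | 29 | ± 2 | 22–43 | 7 | 14 |
| 6 | 57 | ± 3 | 44–60 | 13 | 3 |

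The Visit 6 lower bound follows the midpoint between Visits 5 and 6: (29 + 57)/2 = 43, so Visit 6 starts on Day 44. The upper bound is the visit-window limit: 57 + 3 = 60. Only Visit 6 has a late allowance equal to its visit window.

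**2. Against the endpoint.** The window spans 60 − 44 + 1 = 17 days. Days 54 to 60 (7 days) are inside Day 57 ± 3; Days 44 to 53 (10 days) are not. The row therefore follows neither the endpoint definition nor the adjoining-window principle. On the early side, protocol Appendix 1 puts early termination in the Visit 6 column, and protocol section 8.4.11 collects VAS and fluorescein staining there. A withdrawal visit on Days 44 to 53 could thus count as an observed Week 8 value, while a completer seen on Day 61 is imputed.

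**3. What happens to a Day 61 value.** No window contains it and no rule assigns it. If the subject has no other value in Days 44 to 60, Visit 6 is empty and section 2.6 applies. The missing-at-random category there is worded around withdrawal, so it does not clearly name a completer who was merely late.

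**4. Reproducing the SAP's power.** The SD and difference are redacted, so I solve for the standardized difference d from 99.4% power at 135 per arm, two-sided 0.05: d = (1.960 + 2.512)/√(135/2) = 0.544. At 119 per arm, Φ(0.544 × √(119/2) − 1.960) = 98.7%, which matches SAP section 5.

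**5. Size, over an assumed late share q of completers.** With the planned 10% dropout, observed n per arm = N × 0.9 × (1 − q) and missingness = 1 − 0.9 × (1 − q). Power uses observed values only, with no credit for earlier visits.

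| q | Missing | Late among 270 completers | Power, N = 150 per arm | Power, N = 130 per arm |
|---|---|---|---|---|
| 0 | 10.0% | 0 | 99.4% | 98.6% |
| 1% | 10.9% | about 3 | 99.4% | 98.6% |
| 2% | 11.8% | about 5 | 99.3% | 98.5% |
| 5% | 14.5% | about 14 | 99.2% | 98.2% |
| 10% | 19.0% | 27 | 98.9% | 97.7% |

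The last column uses 130 × 0.9 = 117 completers per arm; the SAP prints 119.

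**6. The 10% condition.** Planned dropout of 10% already just meets a threshold of at least 10%. Late visits decide this condition where actual dropout is a little lower. With an assumed 8% dropout, missingness reaches 10% at q = 1 − 0.90/0.92 = 2.2%.

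**7. Possible bias.** Bias is the late share times the gap between the late subjects' true arm difference and the imputed one. The documents give neither. With an assumed gap of 0.5 SD and late shares of 2%, 5% and 10%, it is 0.01, 0.025 and 0.05 SD.

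**The case against.** The best defence is that Day 60 is the endpoint's own upper limit, so the cut-off respects the estimand. That holds for the late side taken alone. It does not justify the row, which admits ten days outside the same definition on the early side.

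Four stronger readings are tempting, and the documents do not support them.

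- A reader might infer that the cut-off contradicts the treatment-policy strategy as such. That strategy covers three named events, and lateness is not one of them; "Measures will be analyzed regardless of treatment compliance" concerns dosing, not visit timing. The conflict is narrower. It arises when a subject who stopped study drug, was non-compliant or used prohibited medication is measured only after Day 60, because the SAP promises to analyze such measures.
- A reader might infer that every outcome after Day 60 is expressly discarded and imputed. The SAP is silent on values outside all windows. Loss is the natural reading, and a subject with another value in Days 44 to 60 is not missing.
- A reader might infer that late visits alone trigger Estimand 2. SAP section 2.6 also requires an imbalance on EDS-VAS (Fisher p < 0.05), so evenly spread late visits would not by themselves trigger it.
- A reader might infer a material loss of power. The table above shows otherwise.

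It is also fair to object to an unlimited upper bound. Visit 5 dispenses two kits (protocol section 8.4.6) of 17 one-day pouches each (protocol section 11.5.1): 34 days from Day 29, that is through Day 62. Protocol section 8.4.10 lets unscheduled visits include any assessment the investigator judges necessary, so with no limit a much later result could become Week 8. This argues for a stated bound or for nominal Visit 6 results, not for stopping at Day 60.

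**Conclusion.** The point holds as an inexpensive improvement. As written, the window can lose observed ITT primary outcomes under a rule that fits neither Day 57 ± 3 nor the pattern of the other windows, and handling outside all windows is unspecified. The effect on CCSS power is small: at 10% late, about 0.5 points at 150 per arm and about 1 point at 130 per arm. The more visible effect is on missingness, 10.9% to 19.0% for late shares of 1% to 10%, which bears on one of the two conditions for Estimand 2. These sizes rest on an assumed late-visit rate, the planned 10% dropout, and a standardized difference inferred from the stated power. Any bias depends on an unknown departure and is illustrative only.

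**What to change.** - Extend the Visit 6 upper bound so that observed nominal Visit 6 results are kept: for example Day 44 to Day 70, symmetric with the early side (57 + 13 = 70), or nominal Visit 6 whenever held. Keep the closest-to-Day-57 rule.
- State how efficacy values outside all windows are handled.
- Add a sensitivity analysis restricted to Days 54 to 60, so that both early and late values are tested against the endpoint's Day 57 ± 3.
- Leave out-of-window visits as protocol deviations, a category already in SAP section 9.2, for the per-protocol analysis.

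The cost is one table cell, a few sentences and one extra table per primary endpoint. The downside is that a few later measurements, some possibly after study drug supply has run out, enter the Week 8 mean. Visits 7 to 9 in SAP Appendix 2 collect no VAS or staining, so the change draws in no data from them.

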3.2 Schedule of Visits and Assessments

The schedule of visits and assessments is provided in [Appendix 2](#).

4. Study Treatments

4.1 Method of Assigning Subjects to Treatment Groups

Prior to initiation of study run-in at Day -14, each subject who qualifies for entry will be assigned a screening number. All screening numbers will be assigned in strict numerical sequence at a site and no numbers will be skipped or omitted. If all inclusion criteria are met and none of the exclusion criteria are met at Day -14 and Day 1, each qualifying subject will then be assigned a randomization number (assigning them to Tanfanercept Ophthalmic Solution 0.25% or Placebo Ophthalmic Solution) at the end of Day 1 using the Interactive Response Technology (IRT). The randomization number will be recorded on the Subject's source document and the electronic Case Report Form (eCRF) .

The randomization number will be recorded on the Subject Record Page and eCRF. A new kit will be dispensed at Day 1, Day 15, and Day 29 based on the subject's randomization. The Day 1 kit will be re-dispensed at Day 8. At Day 29, subjects will receive two assigned study drug kits with sufficient supply to last until Day 57. The Sponsor, investigators, and study staff will be masked during the randomization process and throughout the study.

4.2 Masking and Unmasking

All subjects, investigators, and study personnel involved with the conduct of the study will be masked with regard to treatment assignments. When medically necessary, the investigator may need to determine what treatment arm has been assigned to a subject. When possible (i.e., in non-emergent situations), Ora and/or the study sponsor should be notified before unmasking study drug. The unmasked subject will be discontinued from the study.

5. Sample Size and Power Considerations

The primary objective of the study is to demonstrate a statistically significant difference between the active treatment and placebo.

Per the protocol, this study was expected to randomize 150 subjects in each of the two treatment arms, for a total of 300 randomized subjects. Assuming a 10% drop out rate, 135 subjects per group are expected to complete the study.

Assuming a common standard deviation (SD) in the change from baseline (Day 1) to Day 57 for CCSS of [REDACTED] a sample size of 135 evaluable subjects per group will have 99.4% power to detect a difference of [REDACTED] between the active treatment group and the placebo group at a significance level of 0.05.

After randomizing 260 subjects, the Sponsor conducted a masked interim assessment of the sample size ([section 3.1](#)). The power was recalculated based on the reduced sample size following the original assumptions described above.

After randomizing 130 subjects in each of the two treatment arms, for a total of 260 randomized subjects and assuming a 10% drop out rate, 119 subjects per group are expected to complete the study.

Assuming a common standard deviation (SD) in the change from baseline (Day 1) to Day 57 for CCSS of [REDACTED] a sample size of 119 evaluable subjects per group will have 98.7% power to detect a difference of [REDACTED] between the active treatment group and the placebo group at a significance level of 0.05.

6. Data Preparation

All the datasets used for the analyses and presentations of summary results will be implemented using Clinical Data Interchange Standards Consortium (CDISC, Implementation Guide [IG] Version 3.2) and the analysis data model (ADaM, Implementation Guide [IG] Version 2.0) format. The ADaM datasets will be created using SDTM datasets.

7. Analysis Populations

The following analysis populations will be considered:

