16.1.2 ORA CALIBRA® DROP COMFORT QUESTIONNAIRE

Descriptions of drop comfort will be assessed at 3 minutes following initial dosing at Day 1 and Visit 3 (Day 8) using the Ora Calibra® Drop Comfort Questionnaire. On this questionnaire, subjects will be asked to choose three words that best describe how each eye drop feels in both of his/her eyes. [REDACTED]

[REDACTED] Subjects may also select "other" and write in a response of their choosing, which may be either a positive or a negative response. Drop Comfort Questionnaire responses will be summarized by treatment group using qualitative summary statistics. Subjects with at least one negative response as well as subjects with at least one positive response will also be summarized by treatment group. Analyses will be performed on the ITT population with observed data only.

17. Interim Analyses

No interim analyses are planned for this study.

18. Changes from Protocol-Stated Analyses

There are no changes from the protocol-stated analyses.

19. References

20. Revision History

Revision history will be documented for any change in the organization responsible for SAP authorship and after the final execution of Version 1.0 of this SAP.

21. Tables

Ten tables that will be included in the topline delivery are shown in boldface font.

^{1,2} One of the two sets of primary endpoint tables will be delivered with topline according primary estimand defined in [section 2.6](#).

Table Number	Title	Population
Table 14.1.1	Subject Disposition	All Randomized Subjects
Table 14.1.2.1	Demographics	ITT Population
Table 14.1.2.2	Demographics	Safety Population
Table 14.1.3.1	Baseline Disease Characteristics (Study Eye)	ITT Population
Table 14.1.4.1	Ocular Medical History	ITT Population
Table 14.1.4.2	Non-Ocular Medical History	ITT Population
Table 14.1.5.1	Ocular Concomitant Medications by Treatment Group, Drug Class, and Preferred Name	ITT Population
Table 14.1.5.2	Non-Ocular Concomitant Medications by Treatment Group, Drug Class, and Preferred Name	ITT Population
Table 14.1.6.1	Ocular Concomitant Procedures	ITT Population
Table 14.1.6.2	Non-Ocular Concomitant Procedures	ITT Population
Table 14.1.7	Subject Pooling by Site	All Randomized Subjects
Table 14.2.1.1	Central Corneal Fluorescein Staining (Ora Calibra Scale) at Visit 6 (Day 57)	ITT Population with Multiple Imputation

Table Number	Title	Population

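### SAP Section 5 states 119 completers per group, but its own 130 per arm and 10% dropout give 117, and the readable text of SAP Section 3.1 still describes about 300 subjects.

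*SAP*

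**What the plan says.** SAP Section 5 gives two sets of sample-size figures.

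- **As planned in the protocol.** It recalls that "this study was expected to randomize 150 subjects in each of the two treatment arms, for a total of 300 randomized subjects". It continues: "Assuming a 10% drop out rate, 135 subjects per group are expected to complete the study". Power follows: "a sample size of 135 evaluable subjects per group will have 99.4% power to detect a difference of" a redacted amount. Protocol Section 10.3 has the same figures.
- **After the reduction.** Once 260 subjects had been randomized, "the Sponsor conducted a masked interim assessment of the sample size", with a pointer to SAP Section 3.1. Power was then recalculated under the original assumptions. With 130 randomized per arm, the restated expectation reads: "for a total of 260 randomized subjects and assuming a 10% drop out rate, 119 subjects per group are expected to complete the study". The power given for that number is 98.7%.

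SAP Section 3.1 lists about 150 per arm and says: "Approximately 300 subjects will be randomly assigned to one of two treatment groups (1:1"). Its readable text contains no account of the masked assessment. A figure at the end of that section is not reproduced in the text available for review.

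SAP Section 17 says that no interim analyses are planned. SAP Section 18 says: "There are no changes from the protocol-stated analyses".

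**The concern.** The completer count for the reduced trial does not follow from the two numbers printed beside it, and the power for the reduced trial was calculated at that count. The planned size, the evaluable number and the power are figures that a study report normally repeats, so the slip would probably be carried forward.

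Separately, the SAP carries two sample sizes. Section 5 works with 260. The design section, where a reader looks for the current trial size, still has about 300. The pointer from Section 5 to Section 3.1 leads to no readable description of the assessment.

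At stake is whether the SAP's stated figures agree with one another. The type I error and the adequacy of the sample size are not in question.

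**Working it through.** **Inputs (SAP Section 5 unless noted)**

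- Planned: 150 per arm, 10% dropout, 135 completers, 99.4% power.
- Reduced: 130 per arm, 10% dropout, 119 completers, 98.7% power.
- Significance level 0.05, two-sided (SAP Section 8.4); 1:1 allocation (SAP Section 3.1).
- SD and difference: redacted, and said to be unchanged between the two calculations.

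**Step 1. Completers = randomized × (1 − dropout)**

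- Planned: 150 × 0.90 = 135. This reproduces the stated figure exactly.
- Reduced: 130 × 0.90 = 117. The stated figure is 119.

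**Step 2. Could another rule give 119?**

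- Implied dropout: 1 − 119/130 = 8.5%, which is not stated.
- Dividing by 1.1: 130/1.1 = 118.2, or 119 if rounded up. The same rule turns 150 into 136.4, not 135, so it does not explain both figures.
- Working backwards at 10%: 119/0.90 = 132.2, which needs 133 randomized per arm, not 130.

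None of these rules gives both 135 and 119 from the stated inputs.

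**Step 3. Which n does 98.7% belong to?**

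Because the SD and difference are redacted, solve for the standardized difference d that gives 99.4% power at 135 per arm. With the normal approximation:

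d = (1.960 + 2.512) / √(135/2) = 4.472 / 8.216 = 0.544

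Power at n per arm is Φ(d√(n/2) − 1.960):

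- n = 119: 0.5443 × 7.714 − 1.960 = 2.239, power 98.74%.
- n = 117: 0.5443 × 7.649 − 1.960 = 2.203, power 98.62%.

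The noncentral t gives d = 0.546, with power 98.73% at 119 and 98.61% at 117. The stated 98.7% is therefore reproduced at the stated n of 119.

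**Step 4. Range for power at 117**

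The stated powers are rounded, so d is known only within limits (noncentral t).

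| Constraint on d | Power at 117 per arm |
|---|---|
| 99.4% at 135 only | 98.5% to 98.7% |
| 99.4% at 135 and 98.7% at 119 | 98.52% to 98.63% |

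When both stated powers must hold, power at 117 prints as 98.5% or 98.6%.

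**Step 5. Trial size**

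300 − 260 = 40, and 40/300 = 13%. This is the gap between the text of SAP Section 3.1 and SAP Section 5.

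**The case against.** The best case against the point is that it is tiny. The gap is 2 subjects per arm and about 0.1 point of power, and 98.7% is correct for the 119 that is printed. All randomized subjects enter the primary analysis, so no test, population or decision rule depends on the assumed completer count. The 300 in Section 3.1 is labelled approximate and matches the protocol, so it reads as design text that was not updated. All of this stands and sets the weight of the point. It does not make 119 follow from 130 and 10%.

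Three stronger readings are tempting, and the documents do not support them.

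- **That the SAP hides or denies the reduction.** Section 5 sets out the planned size, the masked assessment and the reduced size side by side, each labelled.
- **That Sections 17 and 18 contradict Section 5.** Section 17 concerns interim analyses, and a masked review of sample size with no treatment comparison need not be one. Section 18 concerns changes to analyses, not to enrolment.
- **That Section 3.1 says nothing about the assessment.** Only its readable text is silent. The figure at the end of the section was not available, so a description there cannot be excluded.

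**Conclusion.** The point holds as a minor inconsistency in two parts.

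First, on the SAP's stated inputs the expected number of completers is 117 per group, and the 98.7% power belongs to 119. This rests only on the printed 130 and 10%, neither of which is redacted. The corresponding power of about 98.5% to 98.6% assumes a two-sample comparison of means, two-sided at 0.05, with the same SD and difference in both calculations. It is back-solved from rounded powers, so the exact figure is for the sponsor to supply.

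Second, the readable design text in SAP Section 3.1 (about 300, about 150 per arm) does not match the 260 (130 per arm) in Section 5.

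Neither part suggests an underpowered trial or an effect of the masked assessment on the type I error.

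**What to change.** - **SAP Section 5:** state 117 completers per group and have the sponsor recompute the power from the unredacted SD and difference. If 119 was intended, state the 8.5% dropout that it implies and say where that rate comes from; 98.7% can then stay.
- **SAP Section 3.1:** replace about 300 and about 150 per arm with 260 and 130 per arm, or label the larger figures as the protocol's plan. Check that the cross-reference from Section 5 leads to a description of the masked assessment.
- **Optional:** add a sentence in Sections 17 and 18 saying that a masked sample-size assessment took place and, if this is so, that it involved no treatment comparison.

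The cost is wording only. The stated power falls by about 0.1 point if 117 is used, and no analysis changes.
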